1.2.1 End-points for secondary objectives

The secondary variables are:

Mean change of tumor volume assessed by pituitary MRI from baseline to Week 4, 12, 24, 48, 72 and
 96.

- Percent change of tumor volume assessed by pituitary MRI from baseline to Week 4, 12, 24, 48, 72 and
 96.
- Proportion of patients achieving tumor volume reduction of at least ≥ 20% after 4, 12, 48, 72 and 96 weeks of treatment.
- Time to treatment response for treatment responders, defined as the time from the date of first injection to the first evaluation the patient achieves tumor volume reduction of at least >20%.
- Change from baseline to Week 4, 12, 24, 48, 72 and 96 in disease-related symptoms scores.
- Incidence of pituitary hormonal dysfunction at baseline and at Weeks 4, 12, 24, 48, 72 and 96.
- Proportion of patients achieving alpha subunit reduction of at least 50% at Weeks 4, 12, 24, 48, 72 and 96.
- Proportion of patients achieving normalization of alpha subunit at Weeks 4, 12, 24, 48, 72 and 96.
- Percentage of CTC (≥3) adverse events during treatment with pasireotide LAR.
- Percentage of patients with at least one adverse event with CTC grade ≥ 3.
- Incidence of all adverse events, incidence of laboratory abnormal values and summary of laboratory assessments.
- For extension phase: among patients who had been considered as responsive (*i.e.*, patients who achieved a reduction in tumor volume of at least 20% with respect to the initial tumor volume), assess the number and proportion of patients that remained responsive during the treatment period of extension phase (according to estimates by magnetic resonance at weeks 48, 72 and 96).
- To assess the percentage of patients who remained with tumor volume stable during the study, *i.e.* patients who maintained tumor volume with variation less than 20% with respect to the basal tumor volume (according to evaluations by magnetic resonance imaging at weeks 24, 48, 72 and 96).
- If applicable, assessing whether there was difference in response between patients using dose of 40 and 60 mg of pasireotide LAR.

2 Study design

This is a prospective, multicenter, open-label, single arm, phase II study to evaluate the efficacy and safety of pasireotide LAR in adult patients with NFPA.

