Eligible patients will receive pasireotide LAR 60 mg every 28 ± 3 days for 24 weeks, during the Core Phase of the study. The study is complimented by an extension. As per treating physician' discretion, patients who have benefited from the treatment with pasireotide LAR can enter an Extension Phase where they will continue to receive pasireotide LAR 60 mg at 4-week (\pm 3 days) intervals for up to 2 years or until pasireotide or other effective therapy becomes commercially available or until clinical benefit is noted (whichever comes first). Dose reductions to 40 mg will be permitted based on safety issues. In case of rapid deterioration of the visual field or sudden visual loss, the patient will be discontinued from the study.

During the Core Phase of the study, visits will be performed every 28±3 days. There will be two extra visits: Visit 3 and Visit 6.

The design of the study and a schematic of the Core Phase and Extension Phase are presented in **Figure 1** and **Figure 2**, respectively.

Figure 1 Schematic of the Pasireotide LAR Study of NFPA: Core Phase

[figure not shown]
[figure not shown]

Figure 2 Schematic of the Pasireotide LAR Study of NFPA: Core Phase

^{*}Details of efficacy and safety evaluation, presented in Table A1.

3 Population

The population for this study is adult patients with a diagnosis of NFPA who have not undergone any prior therapy (treatment-naïve) for the disease. As tumor volume changes are difficult to be evaluated in microadenomas and also because they may be misdiagnosed with incidentalomas, only patients with macroadenomas (≥ 1 cm) will be included. A total of 23 patients in 10-13 centers will be enrolled in this single-arm open-label study.

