5.5.3.1 Adverse events

All AEs recorded during the study will be summarized. The incidence of treatment-emergent AEs (new or worsening from baseline) will be summarized by system organ class, severity (based on CTCAE grades), type of AE, relation to the study drug. Deaths reportable as SAEs and non-fatal serious adverse events will be listed by patient and tabulated by type of AE.

Treatment-emergent adverse events (TEAEs) will include all adverse events who started between first and 28 days after the last administration of study medication.

5.5.3.2 Laboratory abnormalities

All laboratory values will be converted into SI units and the severity grade calculated using appropriate Common Toxicity Criteria (CTC).

Frequency of laboratory abnormalities will be displayed by parameter and study day. Notably abnormal laboratory values (new or worsening from baseline based on CTC grades) will be summarized by laboratory parameter. Shift tables will be presented comparing baseline laboratory result (CTC grade) with the worst result (expressed in CTC grade) during study. Patient with abnormal laboratory values will be listed and values outside the normal ranges will be flagged. A separate listing of laboratory abnormalities of CTC grade 3 or 4 will also be provided.

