Table 14 – Gallblader ultrasound – FAS population

	Total	
	(n=xx) V1	V10
Gallblader ultrasound performed, n	9/1	
Yes	70)	
No		
Total		
If yes		
Any gallstones detected, n (%)		
Yes		
No		
Total		
Dilatation of the intra or extra hep	patic	
ductal system, n (%)		
Yes		
No		
Total		
Location of dilatation, n (%)		
Intrahepatic ductal system		
Extrahepatic ductal system		
Total		

Table 15 – Treatment-emergent adverse events and serious adverse events – Safety population

Total (n=xx) Patients with at least one adverse event, n (%)a) Yes Total Patients with at least one serious adverse event, n (%)a) No Total Grade of adverse events, n (%)b) Grade 1 Grade 2 Grade 3 Grade 4 Total Grade ≥ 3 Relationship of study drug, n (%)b) Not suspected Suspected Total Action taken for adverse event, n (%)b) No action taken. Study drug dosage adjusted / temporarily interrupted. Study drug permanently discontinued due to this adverse event Concomitant medication taken Non-drug therapy given Hospitalization / prolonged hospitalization Serious adverse events, n (%)b) Yes No

a) Percentage calculated within the total number of patients of safety population (n=xx).

b) Percentage calculated within the total number of adverse events reported by safety population (n=xxx).

Table 16 – Incidence of treatment-emergent adverse events – Safety population

	Total
	(n=xx)
Incidence of adverse events, n (%)	
Xxxxx	

a) Percentage calculated for total of patients of patients of the safety population (n=xx).

Table 17 – Incidence of serious treatment-emergent adverse events – Safety population

	Total
	(n=xx)
Incidence of serious adverse events, n (%	
Xxxxx	

a) Percentage calculated for total of patients of patients of the safety population (n=xx).

Table 18 – Incidence of treatment-emergent adverse events with suspected relationship with study drug – Safety population

	Total	
	(n=xx)	
Incidence of adverse events with suspected relationship with study drug, n (%)	у	
Xxxxx		

a) Percentage calculated for total of patients of patients of the safety population (n=xx).

Table 19 – Incidence of serious treatment-emergent adverse events with suspected relationship with study drug – Safety population

	Total	
	(n=xx)	
Incidence of serious adverse events with study drug, n (%)	suspected relationship with	
Xxxxx		

a) Percentage calculated for total of patients of patients of the safety population (n=xx).

Table 20 – Treatment-emergent adverse events – Safety population

	Total (n=xx)	

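### The SAP lists the percentage of patients with at least one grade ≥3 adverse event as a secondary endpoint, but no adverse-event table shell reports it

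*SAP*

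**What the plan says.** SAP 1.2.1 gives two grade ≥3 endpoints one after the other. The first counts events: "Percentage of CTC (≥3) adverse events during treatment with pasireotide LAR". The second counts patients: "Percentage of patients with at least one adverse event with CTC grade ≥ 3". The protocol synopsis and protocol 3.2.1 carry the same pair, and the list of clarifications in SAP section 7 drops neither.

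The analysis text in SAP 5.5.3.1 says that the incidence of treatment-emergent events "will be summarized by system organ class, severity (based on CTCAE grades), type of AE, relation to the study drug". It names no grade cut-off and no denominator.

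The shells use two denominators in Table 15:

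- Footnote a, "Percentage calculated within the total number of patients of safety population (n=xx", is attached to two items only: patients with any adverse event and patients with any serious adverse event.
- Footnote b, "Percentage calculated within the total number of adverse events reported by safety population", is the event denominator. It is attached to the grade block, which reads "Grade of adverse events, n (%)b) Grade 1 Grade 2 Grade 3 Grade 4 Total Grade ≥ 3", and to relationship, action taken and seriousness.

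Table B 9 repeats this layout for the extension. SAP section 6 points to these two appendices as the place where the study results are presented.

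**The concern.** Listing the two endpoints separately shows that the sponsor regards them as different quantities and wants both. If the tables are programmed from the shells, the report will contain the event percentage and nothing for patients, so a listed secondary safety endpoint would go unreported in both phases.

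The event percentage does not describe a patient's risk. Its denominator grows with every mild event recorded. With 10 grade ≥3 events held fixed, moving from 200 to 400 events in total takes it from 10/200 = 5% to 10/400 = 2.5%, although no patient has fared any better. In a single-arm study there is also no control group against which an event-based percentage could be read.

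**Working it through.** The documents give no adverse-event rate, so there is no planned figure to reproduce. The check has two parts.

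**1. Tracing both endpoints through the shells**

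| SAP shells | Denominator | Split by grade? | Endpoint delivered |
|---|---|---|---|
| Table 15, any AE and any SAE | Patients (footnote a) | No | Neither |
| Table 15, grade block | Events (footnote b) | Yes, with a ≥3 line | Event-level |
| Tables 16–19 | Patients | No | Neither |
| Tables 20–23 | Events | No | Neither |
| Table B 9, any AE and any SAE | Patients (footnote a) | No | Neither |
| Table B 9, grade block | Events (footnote b) | Yes, with a ≥3 line | Event-level |
| Tables B 10–B 13 | Patients | No | Neither |
| Tables B 14–B 17 | Events | No | Neither |

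The patient-level tables 16–19 state their denominator as "Percentage calculated for total of patients of patients of the safety population (n=xx", but none carries a grade column or row. The SAP's list of tables has no adverse-event table by grade. The event-level endpoint is therefore covered in both phases, and the patient-level endpoint in neither.

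**2. Whether the missing figure can be recovered from the event percentage**

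From the documents: N = 23, the planned enrolment in SAP section 3 ("A total of 23 patients in 10-13 centers will be enrolled in this single-arm open-label study"). It is used here as the size of the safety set. All event counts below are assumed.

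*Range for one set of counts.* Take 200 events, 10 of them grade ≥3.

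- Event percentage: 10/200 = 5%.
- All 10 in one patient: 1/23 = 4.3% of patients.
- One in each of 10 patients: 10/23 = 43.5%.
- An intermediate case, 8 patients: 8/23 = 34.8%.

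*Range across event burdens.* Let m be the number of events per patient and q the proportion of events that are grade ≥3. If grades are independent between events, the patient percentage is 1 − (1 − q)^m.

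| m | q = 2% | q = 5% | q = 10% |
|---|---|---|---|
| 5 | 9.6% | 22.6% | 41.0% |
| 10 | 18.3% | 40.1% | 65.1% |
| 20 | 33.2% | 64.2% | 87.8% |

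The column heading is the event percentage and the cell is the patient percentage. In these cases the patient figure is about 4 times (41.0/10) to 17 times (33.2/2) the event figure.

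*A case in the other direction.* Take 46 events, 10 of them grade ≥3 and all in one patient. The event percentage is 10/46 = 21.7% and the patient percentage is 1/23 = 4.3%.

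The event percentage thus fixes neither the size of the patient percentage nor which of the two is larger.

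**The case against.** The best case for the SAP is that its text already commits to the output. Section 1.2.1 keeps the endpoint, and 5.5.3.1 promises incidence by severity. The tables titled as incidence (16–19) all use patients, so incidence by severity reads naturally as a patient-level summary. Section 7 requires departures from the SAP to be accepted by the sponsor and documented, so the endpoint could not simply lapse. Adverse events are recorded by patient and by grade (protocol 7.5.1), so the figure can be computed at any time. The event table also prints n, and 10 events cannot lie in more than 10 patients.

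Most of this stands. A reader might infer that the endpoint has been abandoned, and the documents do not support that. They show shells that do not match the text. The mismatch still matters because section 6 makes the appendices the output and no shell there implements the promise. The printed n gives only an upper limit on the number of patients, as the 4.3% to 43.5% range shows.

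Damage in the PDF text is a fair second objection. In Table 15 the first block has lost its *No* line and the serious-event block its *Yes* line, and the first block of Table B 9 has also lost its *No* line. A lost row cannot be excluded with certainty. However, the grade block is legible in both tables, its ≥3 line sits under footnote b both times, and no table title points to a patient-level table by grade. If the source file does contain such a row, the point falls away.

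**Conclusion.** The point holds as a gap between the SAP's endpoint list and its shells: the patient-level grade ≥3 endpoint in 1.2.1 has no row in Appendix 1 or Appendix 2, and it cannot be derived from the row that is there. It concerns one secondary safety endpoint in a proof-of-concept study. The primary analysis and the sample size are untouched.

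Three stronger readings are tempting and are not supported.

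- **That footnote b is a mistake.** It is the right denominator for the other listed endpoint, and the existing row should stay.
- **That Table 15 makes severe toxicity look far lower than it is.** It may, but the size of the gap rests entirely on assumed counts, and the direction reverses when severe events cluster in few patients.
- **That the tolerability conclusion rests on this row.** SAP 5.5.4 bases tolerability on dose reductions and drug-related events in the safety population. Table 15 also gives any adverse event and any serious adverse event by patient, and Tables 16–19 are by patient.

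The illustrations assume a safety set of 23 and the event counts stated. The finding itself depends on neither, only on the shells being as they read.

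**What to change.** Keep the event-based Grade ≥ 3 row in Tables 15 and B 9. Add to each a row such as *Patients with at least one grade ≥3 adverse event, n (%)* under footnote a, next to the two existing patient-level rows, so that the shells match SAP 1.2.1. State in 5.5.3.1 that this row is the patient-level summary for that endpoint.

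Two additions are optional, since neither is a listed endpoint: an exact confidence interval, at the 95% level announced in SAP section 7, and a matching row for events suspected to be related to study drug. For the assumed 8 of 23 patients the exact 95% interval would be 16.4% to 57.3%.

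The cost is one row in each of two tables and one sentence of text. No new data are needed, because grade is already recorded for each event in each patient.

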#### 6.4.5 Early patient discontinuation

#### 6.4.5.1 End of treatment

Patients may withdraw voluntarily from the study or be withdrawn, at the investigator's discretion, at any time. They may be considered as discontinued if they declare their intention to discontinue, or if they do not return for visits, or if they are lost to follow-up for any other reason. Patients may be withdrawn from the study by the investigator for any of the following reasons:

- Acute or progressive vision loss confirmed by a new evaluation of the visual field
- Increased tumor volume defined as tumor volume growth (>20%) and confirmed in a second MRI performed approximately one month later
- Pregnancy
- Adverse event(s)
- Uncontrolled diabetes mellitus
- Clinically significant abnormal laboratory value(s)
- Clinically significant abnormal result(s) of test procedures
- Protocol violation
- Lost to follow-up
- Administrative problems
- Death
- Patients who experience:
- ALT or AST > 3 x ULN and Total Bilirubin  $\ge 2$  x ULN and ALP < 2 x ULN
- ALT or AST > 5 x ULN and  $\le 8$  x persistent ULN for more than 2 weeks
- ALT or AST > 8 x ULN

If any of the discontinuation criteria is met, the study medication must be immediately discontinued. Additionally, appropriate safety follow-up monitoring must be performed, as defined on Section 7.5.2.3. Resuming the study medication after the discontinuation criteria are met is not allowed.

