#### 7.5.6.3 Chemistry

A complete chemistry profile will be evaluated in the screening period and before administration of the study drug on each visit (except on Visit 2, Visit 3, Visit 6, and Visit 11, the Follow-up Visit) and will include: total cholesterol, low density lipoprotein (LDL) cholesterol, high density lipoprotein (HDL) cholesterol, triglycerides, calcium, phosphorus, chloride, sodium, potassium, inorganic phosphorus, creatinine, urea, uric acid, CPK, LDH, alkaline phosphatase,  $\gamma$ -GT, total protein, albumin, SGOT, SGPT, total bilirubin. In the Extension Phase, the chemistry profiles will be evaluated on visit 10 (Week 24) and then every 6 months thereafter (Weeks 48, 72, and 96).

[figure not shown]
If total bilirubin concentration increases more than 2.0 times the upper limit of normal, total bilirubin must be differentiated in direct and indirect reagent bilirubin on all visits.

Fasting blood glucose, insulin, and fasting chemistry evaluations will be performed in the screening phase and before administration of the study drug on each visit, except on Visit 2, Visit 3 (Week 3), Visit 6 (Week 11), and Visit 11 (Week 28, Follow-up Visit) in the Main Phase; they will also be performed on Weeks 48, 72, and 96 in the Extension Phase.

Liver function tests (ALT, AST, total bilirubin, albumin, ALP, and  $\gamma$ -GT) will be evaluated on visit 1 (screening), visit 2 (baseline), visit 6, and visit 10 for all patients. Liver function tests will also be evaluated on visit 3, visit 4, visit 401 (after 48 days), and visit 5.

HbA1c evaluations will be performed in the screening period (these will be considered as baseline data), on Weeks 12 and 24 in the Main Phase, and on weeks 48, 72, and 96 in the Extension Phase.

Vitamin B12 and folic acid evaluations will be performed in the Screening Period (these will be considered as baseline data), on Week 24 in the Main Phase, and on weeks 48 and 96 in the Extension Phase.

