Symptom assessment/ Disease-related symptoms ⁴ (D)	х	х	Х	х	Х	х	Х	Х	х	х	Х	
ECOG performance status (D)	х	х	Х	х		х	Х	Х	х	х	Х	Х
ECG ¹⁴ (D)	х	х	Х	х		х	Х	х	х	Х	Х	
Serum pregnancy test 5,6	х							х			Х	
Hematology (BD)	х			х		х		х	х	х	Х	
Coagulation parameter PT (D)	х	Х	X ¹⁴	X ¹⁴	X ¹⁴	X ¹⁴	х				Х	
Coagulation parameter APTT (D)	х	Х					х				Х	
Urinalysis ⁶ (D)	х			x		х		х	x	х	Х	
Fasting Blood Glucose, Insulin ⁶	х			x		х		х	x	х	х	
HbA1c ⁶	х							х			Х	
Biochemistry ^{6,8} (D)	Х			х		х		х	Х	х	Х	
LFTs (ALT, AST, total bilirubin, albumin, ALP, γ-GT) (D)	х	х	X ¹⁴	X ¹⁴	X ¹⁴	X ¹⁴	Х				Х	
Hbs-Ag and anit-HCV (D)	Х											

Vitamin B12, folic acid ⁶	х										Х	
Hormonal evaluation ^{6,9} (D)	х			х				х			Х	
Alpha subunit evaluation ⁶	Х			х				Х			Х	
Visual field (camp) evaluation 10 (D)	х	X ¹⁰		х		х		х	x	х	Х	
Gallbladder ultrasound (D) 15	Х										Х	
Pituitary MRI / Sella turcica ¹⁵	Х			х				Х			Х	
Adverse events (D)		Х	Х	х	Х	х	Х	Х	х	х	Х	
Pasireotide LAR administration (D)		х		х		х		Х	x	х	X#	
Prior/Concomitant medications ¹¹ (D)	х	х	Х	х	Х	х	Х	Х	Х	х	Х	
Study completion ¹³ (D)												X ¹³

Pasireotide dose on this visit will be administered to selected patients, as per physician discretion, if the patient will be included in the Extension Phase based on response assessed by investigator/ benefit with the drug.

 $^{^{1}}$ Will be allowed a window of \pm 3 days for the planned visits and assessments, unless otherwise specified.

 $^{^{2}}$ It will be allowed a window of \pm 3 days for the planned visits and assessments, unless indicated otherwise.

³ To be completed prior to study drug administration

⁴ To be completed if the patient discontinues prematurely or at study completion.

⁵ Disease related symptoms that will be evaluated: headache, visual disturbances, fatigue, decreased libido, erectile dysfunction (for males only), irregular or stopped menses (for not post-menopausal female only). The investigator will also ask the patient to score the symptoms according to a five-point score scale (0=absent, 1=mild, 2=moderate, 3=severe, 4=very severe). The others will be assessed as present or absent.

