Minimum												
Maximum												
Normal												
Abnormal												
CS												
NCS												

	Total														
	(n=xx)	\/A	VE	V7	V0	V0	V10								
	V1	V4	V5	V7	V8	V9	V10								
asting blood insulin (μlU/mL))															
N															
Mean															
Median															
Standard Deviation															
Minimum															
Maximum															
Normal															
Abnormal															
CS															
NCS															
asting blood glucose (mg/dL)															
N															
Mean															
Median															
Standard Deviation															
Minimum															
Maximum															
Normal															
Abnormal															
CS															
NCS															

Table 28 – Tests for liver function – Safety population

	Total						
_	(n=xx)						
_	V1	V2	V3	V4	V5	V6	V10
SGOT (U/L)							
N							
Mean Median Standard Deviation							
Minimum Maximum							
Normal Abnormal							
CS							
NCS							
SGPT (U/L)							
N			-	-	-		
Mean			-	-	-		
Median			-	-	-		
Standard Deviation Minimum			-	-	-		
Maximum			-	-	-		
Normal			-	-	-		
Abnormal			-	-	-		
CS			-	-	-		
NCS			-	-	-		
Alkaline Phosphatase (U/L)							
N							
Mean Median							
Standard Deviation							
Minimum							
Maximum							
Normal							
Abnormal							
CS							
NCS							

Table 28 (Cont.) – Tests for liver function – Safety population

able 28 (Cont.) – Tests	Total (n=xx)										
	V1	V2	V3	V4	V5	V6	V10				
y-GT (U/L) N											
Mean Median Standard Deviation Minimum Maximum											
Normal Abnormal CS											
NCS											
Fotal bilirubin (mg/dL) N Mean Median Standard Deviation Minimum											
Maximum Normal Abnormal CS											
NCS											
irect bilirubin (mg/dL) N			-	-	-						
Mean Median			-	-	-						
Standard Deviation			-	-	-						
Minimum Maximum			-	-	-						
Normal			-	-	-						
Abnormal CS			-	- -	-						
NCS			-	-	-						

Table 28 (Cont.) – Tests for liver function – Safety population

	Total (n=xx)										
 	, V1	V2	V3	V4	V5	V6	V10				
Indirect bilirubin (mg/dL)											
I											
Лean											
Median											
Standard Deviation											
Minimum											
Maximum											
Normal											
Abnormal											
CS											
NCS											
Albumin (g/dL)											
N											
Mean											
Median											
Standard Deviation											
Minimum											
Maximum											
Normal											
Abnormal											
CS											
NCS											

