Creatinine (mg/dL)				
N				
Mean				
Median Standard Deviation				
Minimum				
Maximum				
Normal				
Abnormal				
CS				
NCS				
Uric acid (mg/dL) N				
Mean				
Median				
Standard Deviation				
Minimum Maximum				
Waximum				
Normal				
Abnormal				
CS NCS				
CPK (U/L) N				
Mean				
Median				
Standard Deviation				
Minimum Maximum				
Normal				
Abnormal CS				
NCS				
104 (1/1)				
LDH (U/L) N				
Mean				
Median				
Standard Deviation Minimum				
Maximum				
Normal				
Abnormal				
CS				
NCS				

```
Total protein (mg/dL)
   Mean
   Median
   Standard Deviation
   Minimum
   Maximum
   Normal
   Abnormal
     CS
    NCS
Total cholesterol (mg/dL)
   Ν
   Mean
   Median
   Standard Deviation
   Minimum
   Maximum
   Normal
   Abnormal
    CS
    NCS
Low density lipoprotein (LDL) cholesterol (mg/dL)
   Ν
   Mean
   Median
   Standard Deviation
   Minimum
   Maximum
   Normal
   Abnormal
    CS
     NCS
High-density lipoprotein (HDL) cholesterol (mg/dL)
   Mean
   Median
   Standard Deviation
   Minimum
   Maximum
   Normal
   Abnormal
    CS
    NCS
Triglycerides (mg/dL)
   Ν
   Mean
   Median
   Standard Deviation
   Minimum
   Maximum
   Normal
   Abnormal
     CS
    NCS
Sodium (mEq/L)
   Ν
   Mean
   Median
```

Standard Deviation Minimum Maximum Normal Abnormal CS NCS Potassium (mEq/L) Ν Mean Median Standard Deviation Minimum Maximum Normal Abnormal CS NCS Calcium (mg/dL) Mean Median Standard Deviation Minimum Maximum Normal Abnormal CS NCS Phosphorus (mg/dL) Mean Median Standard Deviation Minimum Maximum Normal Abnormal CS NCS Chloride (mEq/L) Ν Mean Median Standard Deviation Minimum Maximum Normal Abnormal CS NCS B12 Vitamin (pg/) Ν Mean Median Standard Deviation Minimum Maximum Normal

```
Abnormal
    CS
     NCS
Folic acid (ng/mL)
   Mean
   Median
   Standard Deviation
   Minimum
   Maximum
   Normal
   Abnormal
    CS
    NCS
HbA1c (%)
   Ν
   Mean
   Median
   Standard Deviation
   Minimum
   Maximum
   Normal
   Abnormal
    CS
    NCS
Fasting blood insulin (\mu IU/mL))
   Ν
   Mean
   Median
   Standard Deviation
   Minimum
   Maximum
   Normal
   Abnormal
     CS
    NCS
Fasting blood glucose (mg/dL)
   Mean
   Median
   Standard Deviation
   Minimum
   Maximum
   Normal
   Abnormal
     CS
     NCS
```

CS: Clinically significant; NCS: Not clinically significant.

Table B 22 – Tests for liver function – Safety population

Table B 22 — Tests for liver function — Safety po	Total (n=xx)		
	V16	V22	V28
SGOT (U/L)			
N			

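### SAP Table 28 shows no ALT at the four core visits where Amendment 2 added liver tests, and the by-visit shells also miss Visit 402 and the chemistry-panel ALT and AST at V7-V9

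*SAP*

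**What the plan says.** **Schedule, core phase.** Protocol 7.5.6.3 says the liver panel, which includes ALT, "will be evaluated on visit 1 (screening), visit 2 (baseline), visit 6, and visit 10 for all patients". It then adds: "Liver function tests will also be evaluated on visit 3, visit 4, visit 401 (after 48 days), and visit 5". The liver-test rows of protocol Table 7-1 and SAP Table A 1 mark the same eight visits. Section 11.5.1 ties the additions at days 20, 28, 48 and 56 to Amendment 2 and an internal medical review of the pasireotide studies. It calls the day-48 visit V4L; the schedule tables call it V401.

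The complete chemistry profile also contains both transaminases ("total protein, albumin, SGOT, SGPT, total bilirubin"). Tables 7-1 and A 1 mark it at V1, V4, V5, V7, V8, V9 and V10.

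**Schedule, extension.** SAP Table A 2 marks liver tests at V10, V402, V16, V22 and V28.

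**Shells.**
- "Table 28 – Tests for liver function – Safety population" has columns V1, V2, V3, V4, V5, V6 and V10. Its SGPT block is dashed in every row at V3, V4 and V5. The SGOT, alkaline phosphatase, γ-GT, total bilirubin and albumin blocks are open there.
- Table 27 (biochemistry) has columns for V7-V9 but no SGOT or SGPT rows.
- "Table B 22 – Tests for liver function – Safety population" has columns V16, V22 and V28 only.

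**Text on laboratory display.** SAP 5.5.3.2 states: "Frequency of laboratory abnormalities will be displayed by parameter and study day". It also plans shift tables from baseline to worst grade, a listing of patients with abnormal values, and a separate grade 3 or 4 listing.

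**The concern.** SAP section 6 says the results are presented in the appendix tables, so a programmer will build what the shells show. Elsewhere in the SAP a dash marks a visit where nothing is measured: in Table 33, height is dashed at every visit after V1. Read the same way, the SGPT dashes say that ALT is not assessed at V3-V5, which contradicts the SAP's own Table A 1. SAP section 7 lists the departures from the protocol, and dropping these visits is not among them.

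The gap falls on the visits that matter most for early liver detection. ALT is tabulated at none of the four core visits where Amendment 2 added liver tests. The protocol's liver criteria are written for either transaminase, for example "ALT or AST > 8 x ULN". An open SGOT block therefore does not reveal a rise confined to ALT. Table 28 is also the only core shell with by-visit normal and abnormal counts for ALT, and the incidence of abnormal laboratory values is a listed secondary endpoint (SAP 1.2.1).

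A related gap concerns the joint criterion in protocol 7.5.2.3: ALT or AST above 3 x ULN together with total bilirubin at least 2 x ULN. Summaries made one parameter at a time cannot show how many patients met both parts.

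**Working it through.** The documents give no figure on this point, so there is nothing to reproduce. The check is a count of scheduled visits against open cells.

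**Inputs.** The schedule comes from the X marks in protocol Table 7-1 and SAP Tables A 1 and A 2. The shells are SAP Tables 27, 28 and B 22.

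**Post-baseline core visits**

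| Visit | Liver-test row | Chemistry row | SGPT, Table 28 | SGOT, Table 28 |
|---|---|---|---|---|
| V3 | X | | dashed | open |
| V4 | X | X | dashed | open |
| V401 | X | | no column | no column |
| V5 | X | X | dashed | open |
| V6 | X | | open | open |
| V7 | | X | no column | no column |
| V8 | | X | no column | no column |
| V9 | | X | no column | no column |
| V10 | X | X | open | open |

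- Liver-test row alone: 6 visits. ALT is shown at V6 and V10, so 2/6 = 33.3%. AST is shown at 5/6.
- Liver-test row plus chemistry panel: 9 visits. ALT is shown at 2/9 = 22.2%, AST at 5/9.

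**Adding V1 and V2, where SGPT is open**

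- Liver-test row: 6 + 2 = 8 visits; 4 not shown, 4/8 = 50.0%.
- Combined: 9 + 2 = 11 visits; 7 not shown, 7/11 = 63.6%.

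**Adding the extension.** V402, V16, V22 and V28 add 4 visits, with V10 counted once. Table B 22 shows 3 of the 4.

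- Liver-test row: 8 + 4 = 12 visits; 4 + 1 = 5 not shown, 5/12 = 41.7%.
- Combined: 11 + 4 = 15 visits; 7 + 1 = 8 not shown, 8/15 = 53.3%.

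**Effect of the repair on the combined schedule.** Removing only the V3-V5 dashes gives ALT at 7 of 11 core visits and 10 of 15 overall. Adding V401, V7-V9 and V402 as well gives 11 of 11 and 15 of 15.

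**Are the dashes an artefact of reading the PDF?** That is unlikely. They fill every row of the SGPT block in exactly three columns, while the blocks on either side are open.

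**The case against.** The strongest reply is that this is a proofreading slip in shells that are not exhaustive. Much of that stands.

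- **The values are handled elsewhere.** SAP 5.5.3.2 sends all laboratory results to abnormality frequencies, worst-grade shift tables and two listings, none of them limited to Table 28's columns. With 23 patients in one arm, a listing shows an abnormal ALT directly. This stands, so it would be wrong to infer that the values are lost. However, neither appendix has a shell for those outputs, and the by-visit display that 5.5.3.2 promises is not delivered for ALT.
- **The early visits are not dropped as a whole.** A reader might infer that the added visits vanish from the safety summary. Table 28 has V3, V4 and V5 columns, and every scheduled liver analyte except ALT is open there. Only V401 and V402 are wholly absent.
- **ALT is not the sole trigger.** The criteria read ALT or AST, and AST is open at V3-V5. This narrows the gap to rises confined to ALT.
- **The count depends on the rule.** A reader might say that most scheduled ALT values go untabulated. That holds on the combined schedule. It fails on the liver-test row, where exactly half of the core visits and 5 of 12 overall are not shown. Table 28's columns match that row except for V401.
- **The dashes look clerical.** Direct bilirubin is dashed beside open indirect bilirubin. In Table 25, PT in seconds is dashed at V3-V5 beside open PT in percent, although PT is scheduled there; APTT in percent is open where APTT is not scheduled. The documents do not support reading this as a decision to exclude ALT.
- **The notification count is not promised anywhere.** That is correct. It is a cheap addition, not the repair of a broken commitment.

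**Conclusion.** The point holds as a mismatch between schedule and shell. Table 28 omits ALT at V3, V4, V401 and V5, although the protocol and the SAP's own schedule require it. The other liver analytes lack V401, Table B 22 lacks V402, and no shell carries ALT or AST at V7-V9. By-visit ALT is shown at 2 of 6 post-baseline core visits on the liver-test row, or 2 of 9 with the chemistry panel counted.

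The consequence is limited to safety reporting. The values are absent from the by-visit tables but should still reach the outputs planned in SAP 5.5.3.2. The primary endpoint and every efficacy estimate are untouched.

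The conclusion assumes that the dashes are in the source document, that SGPT and ALT are the same test, and that the schedule is the one marked in Tables A 1 and A 2. The larger count also assumes that transaminases are reported from the chemistry panel at V7-V9, as its definition says.

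**What to change.** 1. In Table 28, remove the SGPT dashes at V3, V4 and V5 and add a V401 column for all liver analytes.
2. Add V7-V9 for the liver analytes drawn with chemistry, either as columns in Table 28 or as rows in Table 27.
3. Add a Visit 402 column to Table B 22.
4. Add one short block counting patients who, at any scheduled or unscheduled visit, meet each of the three criteria in protocol 7.5.2.3, including the joint transaminase and bilirubin criterion. Label these as notification criteria. They differ from the discontinuation criteria in 6.4.5.1, which add an alkaline phosphatase condition to the first criterion and persistence beyond two weeks to the second. The block must not be read as a count of patients meeting the discontinuation criteria.

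All of this uses data already collected. The cost is shell edits and minor extra programming.
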